3.1 Overall Design

The primary objective of this study is to investigate the efficacy of AKL-T01 (Akili Interactive), a remotely-delivered digital cognitive intervention, in targeting and improving cognition and functional outcomes in individuals recovering from COVID-19. The efficacy of the AKL-T01 intervention will be measured relative to a waitlist control group. We hypothesize that the AKL-T01 intervention will show greater efficacy relative to the waitlist control at improving cognitive and daily function in COVID-19 survivors.

To test this hypothesis, adults who were previously infected with a diagnosis of COVID-19 and confirmed history of SARS-CoV-2 infection will be recruited for our study sample. This is a single site study, and all participants will be recruited through Weill Cornell Medicine and the NewYork-Presbyterian Hospital system. We will screen the electronic medical record (Epic) for NYP, Weill Cornell Medicine. Potential participants can also be referred by their doctor. We will also contact potential participants who were previously enrolled in COVID-19 research studies at NYP/WCM and agreed to be contacted for future research opportunities. We will also post flyers at NYP/Weill Cornell Medical Center and other relevant locations in the greater New York City area.

Due to the ongoing threat of COVID-19 and the remote nature of this trial, informed consent will also be obtained remotely. For participants with access to technology that will allow them to consent electronically, the participant and the member of the research team (co-

investigator or trained research assistant) obtaining informed consent will meet over a HIPAA-compliant video conference platform (i.e., Zoom). At the start of this video meeting, the researcher will share their screen and highlight each section of the consent form while discussing it with the participant. After discussing the consent form with the participant, they can then re-read it and sign it via REDCap. These participants will be provided with a PDF of their signed consent form for their records.

For participants without access to technology that would allow them to consent electronically, the participant and researcher will review the consent form over the phone. A copy of the consent form will be mailed or emailed to the participant in advance so that it can be viewed by the participant during the phone call. They will return the signed consent form in a stamped, self-addressed envelope provided by the researcher. These participants will then be mailed a copy of their signed consent form for their records.

To screen prospective participants, we will conduct an initial screening via a secure HIPAA-compliant videoconferencing platform (Zoom). Participants will be queried for inclusion and exclusion criteria. Participants will be administered via Zoom the Oral Trail Making Test, Stroop Test, and the Frontal Systems Behavior Rating Scale (FrSBe). Participants will be eligible for enrollment if they score <1 standard deviation below their age-normed peers on at least one of these three screening tests.

Participants will be randomized into the intervention arm or a waitlist control arm, with an option for the control participants to receive the AKL-T01 intervention at the conclusion of the initial 6-week waitlist period.

All participants (intervention & waitlist control arm): Full assessment visits will take place pre-intervention (baseline) and post-intervention (week 6). During the 6-week intervention period, shorter intermediate assessment visits will take place at weeks 2 and 4. Participants in the waitlist control arm will continue any ongoing self- or provider-based cognitive intervention (or no intervention) during the initial 6-week waitlist period.

Participants in the intervention arm & participants in the control arm who decline the intervention: A full assessment session at will take place at week 10 (4 weeks post-intervention) for longitudinal follow-up.

Participants in the control arm who begin the intervention at the conclusion of the waitlist period: The week 6 assessment visit will also serve as the baseline for the beginning of the intervention. Intermediate assessment visits will take place at weeks 8 and 10, a full post-intervention assessment visit will take place at week 12, and a follow-up assessment visit will take place at week 16 (4 weeks post-intervention).

See Section 6.1 for the complete Schedule of Assessments.

Participants will be aware of their assignment to study arm because it is not possible to blind them. The research team members conducting the study assessments will be blind to assignments. The care managers will not be blinded because it is not possible to blind them and it is necessary for them to know of a participant's assignment to assist in troubleshooting.

Our primary cognitive outcome will be measured by performance on a Digit Symbol Matching Task and our primary functional outcome will be measured by assessment score on the NeuroQOL scale. Additional cognitive tasks will be administered during the assessment visits to measure additional domains of cognition and daily functioning for our secondary and exploratory endpoint analyses. See Schedule of Assessments (Section 6.1) for list of assessments included in battery.

3.2 Scientific Rationale for Study Design

In order to evaluate the efficacy of AKL-T01 for COVID-19, we require comparison to a control group. Because of the potential negative impact of COVID-19 on cognition and functional outcomes, the control arm will be offered the intervention at the end of 6 weeks to ensure all participants ultimately have access to the intervention. Because the control group will not be engaging in any active control condition, there is potential for dropout; however, we will mitigate this dropout via weekly check-ins from the care managers and by providing compensation for those check-in visits to encourage retention.

3.3 Justification for Dose

Participants will complete 6 weeks of the AKL-T01 intervention. Previous research supports improvement of cognition following 4 weeks of the intervention, however continued improvement in a 4 week period after the intervention was observed. However, we are proposing a 6 week intervention to maximize the potential for cognitive change in COVID-19 survivors and because the overall gameplay dose is small (20-25 minutes daily for 5 days a week), and the additional time and remote delivery will not present additional burden to the participants.

3.4 End of Study Definition

A participant is considered to have completed the study for the primary objective of the study if he or she has completed the 6 weeks of the intervention and the post-intervention assessment. For the secondary and exploratory objectives, the end of the study is defined as completion of the week longitudinal follow-up visit.

4. Subject Selection

4.1 Study Population

The study population will be individuals who were diagnosed with COVID-19 (determined by a documented previous positive test results for SARS-CoV-2 infection) and have a deficit in cognition (i.e., attention and/or executive skills > 1 SD below the normal range).

4.2 Inclusion Criteria

1. Male or female 18-89 years of age.
2. Documentation of a deficit in cognitive function (score > 1 standard deviation below normal range) compared to age-adjusted normative data) on at least one screening measure of attention and executive function (Oral Trail Making Test, Stroop Test, or FrSBe).

3. Previous diagnosis of COVID-19 confirmed via SARS-CoV-2 polymerase chain reaction (PCR) test (or reported experience of COVID-19 symptoms with a documented positive antibody test or clinical diagnosis based on symptoms and accompanying physician's note) documented in the electronic medical record or in other existing medical records.
4. Access to and self-report of ability to connect wireless devices to a functional wireless network.
5. Ability to follow written and verbal instructions (English) as assessed by the PI and/or co-investigator.
6. Able to comply with all testing and study requirements and willingness to participate in the full study duration.

4.3 Exclusion Criteria

1. History of neurologic disorder prior to COVID-19 diagnosis, such as Parkinson's disease, multiple sclerosis, Alzheimer's disease, stroke, brain tumor, or dementia.
2. History of severe mental illness (e.g., schizophrenia, psychosis, history of suicide attempt in the last year) or substance use disorder, recent history (in the past year) of alcohol/substance use disorder or symptoms of psychosis.
3. Participant is currently considered at risk for attempting suicide by the Investigator, has made a suicide attempt within the past year, or is currently demonstrating active suicidal ideation or self-injurious behavior.
4. Motor condition (e.g., physical deformity of the hands/arms) that prevents game playing as reported by the participant or observed by the Investigator.
5. Recent history (within 6 months prior to screening/baseline) of substance use disorder.
6. History of seizures (excluding febrile seizures), a tic disorder, significant tics, a current diagnosis of Tourette's Disorder.
7. Color blindness as determined by self-report.
8. Regular use of psychoactive drugs other than antidepressants or benzodiazepines, including stimulants that in the opinion of the Investigator may confound study data/assessments.
9. Any other acute medical condition that may interfere with participation or interpretation of the results.
10. Previous exposure to AKL-T01.

4.4 Lifestyle Considerations

Not applicable.

4.5 Screen Failures

Screen failures are defined as participants who consent to be screened to participate in the clinical trial but are not subsequently randomly assigned to the study because they do not meet inclusion/exclusion criteria. A minimal set of screen failure information is required to ensure transparent reporting of screen failure participants, to meet the Consolidated Standards of Reporting Trials (CONSORT) publishing requirements and to respond to queries from regulatory authorities. Minimal information includes demography, screen failure details, eligibility criteria, and any serious adverse event (SAE).

4.6 Strategies for Recruitment and Retention

We will recruit subjects from the Weill Cornell/NYP system. We anticipate that we will have to screen up to 500 subjects to meet our target enrolment. We will recruit by retrospective review of the electronic medical record, via social media, study flyers and posters, and via referral from providers throughout NYP and WCM. We will attempt to recruit an equal number of males and females; however, anticipate that our sample will reflect current demographic estimates of prevalence of COVID-19, i.e., increased prevalence of severe illness in men. We anticipate that a significant percentage of our sample may be of African American race and/or Hispanic ethnicity due to known racial/ethnic disparities in COVID-19. We will contact patients via contact information listed in the electronic medical record.

We will be recruiting individuals with cognitive impairment because we hypothesize that our intervention has the potential to improve cognitive deficits in this population. We will determine whether participants can sign consent by using teach-back methods to verify comprehension of risks and benefits. We will also use a capacity to consent form (see attachment) to verify comprehension of risks and benefits for subjects deemed to have more than mild impairment based on clinician interview.

Compensation for participation will be provided as follows:

Week	Visit	Compensation * Arm		
		AKL-T01 Intervention	Waitlist Control (No Intervention)	Waitlist Control (Intervention)
0	Pre-Intervention Assessment	\$50	\$50	\$50
2	Intermediate Assessment	\$25	\$25	\$25
4	Intermediate Assessment	\$25	\$25	\$25
6	Post-Intervention Assessment	\$50	\$50	\$50
10	Follow-Up Assessment *	\$75	\$75	
		End of Waitlist		
8	Intermediate Assessment			\$25
10	Intermediate Assessment			\$25
12	Post-Intervention Assessment			\$50
16	Follow-Up Assessment			\$75
Total Per Participant		\$225	\$225	\$325

* Also serves as pre-intervention assessment for waitlist control participants.

5. Registration Procedures

5.1 Subject Registration (WCM only)

Subjects will be registered within the WRG-CT as per the standard operating procedure for Subject Registration.

5.2 Subject Registration (Sub-sites)

Not applicable.

6. Study Procedures

6.1 Schedule of Assessments

Table 1. Schedule of trial events

Measure	Sc	WEEK													
		0	1	2	3	4	5	6	7	8	9	10	11	12	16
Consent	❖														
Demographics	❖														
Medical History	❖														
Cognitive Screen	❖														
Randomization	❖														
Intervention / Check-In		❖	❖	❖	❖	❖	❖	❖	★	★	★	★	★	★	★
Digit Symbol Match		❖		❖		❖		❖	★		❖		★	★	
Multiple Object Tracking		❖		❖		❖		❖	★		❖		★	★	
Digit Span Backwards		❖		❖		❖		❖	★		❖		★	★	
Simple RT		❖		❖		❖		❖	★		❖		★	★	
Choice RT		❖		❖		❖		❖	★		❖		★	★	
Letter/Number Switch		❖		❖		❖		❖	★		❖		★	★	
Gradual CPT		❖		❖		❖		❖	★		❖		★	★	
Visual Paired Associates		❖						❖		○			★	★	
NeuroQOL		❖		❖		❖		❖	★		❖		★	★	
WHODAS (36-item)		❖						❖		○			★	★	
WHODAS (12-item)				❖		❖			★		★				

Modified Fatigue Impact	❖							❖				●		★	★
PHQ-9		❖	❖	❖	❖	❖	❖	❖	★	★	★	●	★	★	★
GADS-7		❖						❖				●		★	★
Adverse Event Monitoring	❖	-----										●		★	★

- ❖ All Participants (Intervention & Control Arm)
- ★ Intervention Arm & No Waitlist Controls ONLY
- Waitlist Controls ONLY

6.1.1 Screening Visit (< 1 week before enrollment and randomization)

Participants will be screened and assessed for eligibility before enrollment and randomization to the intervention and waitlist control arms. During the screening visit, participants will meet via HIPAA-compliant video conferencing platform with a PhD-level member of the study team. During this visit, potential participants will be screened for the cognitive deficit required for participation in the study. Eligible participants will be randomized to the intervention arm or the waitlist control arm in a 1:1 using a computer-generated randomization scheme developed by the data manager at the conclusion of the screening visit. A block randomization approach will be used based on a block of 6.

The screening visit will include the following study procedures:

- Informed consent
- Demographics (in EMR or collected at screening visit)
- Medical / medication history (in EMR or collected at screening visit)
- Additional Medical/Psychiatric symptom screening (completed by member of the research team)
- Cognitive screening (Oral Trail Making Test, Stroop Test, FrSBe)

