2.4.3 Assessment of Potential Risks and Benefits

We will use study procedures designed to maximize the benefit and minimize the risk of participation in this study. Participants in the intervention arm will receive adequate training in gameplay (~45 minute training session with a member of the study team) and have weekly check-ins with trained care managers to troubleshoot issues with the game and monitor gameplay adherence. Participants in the waitlist control arm will also have weekly check-in visits with a care manager.

Assessment sessions will be conducted by PhD-level investigators of this study protocol or Research Assistants who have received extensive training in assessment administration. The assessment battery for this study was optimized to provide measures across a range of cognitive and functional domains that we expect to be impacted in COVID-19 survivors, use well-validated tasks that can be administered remotely, and be as brief as possible to minimize participant burden.

This study will also use a waitlist design to ensure that all participants have the opportunity to receive the benefits provided by the AKL-T01 intervention. At the completion of the 6-week intervention period, participants in the waitlist control group will be given the option to begin 6 weeks of the intervention, which will include the same schedule of weekly check-in and assessment visits.

We expect that the potential benefits of participation outweigh the minimal risks. Participants may experience an improvement in multiple aspects of cognition and daily functioning in COVID-19 survivors. The knowledge gained would inform future clinical trials.

Plan to Address Subjects with Suicidal Ideation and/or Other Mental Health Needs

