6.1.2 Treatment Phase

6.1.2.1 Week 0 (Baseline/Pre-Intervention), Week 6 (Post-Intervention), Week 12 (Post-Intervention; waitlist control participants only)

The pre- and post-intervention visits will take place at the beginning and the end of the intervention period. Participants in both arms will meet remotely with a member of the research team via a HIPAA-compliant video conferencing platform (Zoom). The full battery of cognitive tasks (~35 minutes), functional assessments (~30 minutes), and mood symptom scales (~10 minutes) will be conducted at the baseline visit. Participants in the AKL-T01 intervention arm will be trained in procedures for gameplay during this visit. (Note that the week 6 assessment session will also serve as the baseline assessment for control participants who begin the intervention following the waitlist period.)

The pre- and post-intervention assessment visits will include the following study procedures:

- **Cognitive Tasks:**
- Digit Symbol Matching

- Multiple Object Tracking
- Digit Span Backwards
- Simple RT
- Choice RT
- Letter/Number Switch
- Gradual CPT
- Visual Paired Associates
- **Functional Assessments:**
- NeuroQOL
- WHODAS (36-item)
- Modified Fatigue Impact Scale
- **Mood Symptom Scales:**
- PHQ-9
- GADS-7

6.1.2.2 Weeks 2 & 4 (\pm 2 days; *all participants*) & Weeks 8 & 10 (\pm 2 days; *waitlist control participants only*)

The intermediate assessment visits at weeks 2 & 4 (and weeks 8 & 10 for waitlist control participants) will include a shorter battery of cognitive tasks (~25 minutes) and functional assessments (~10 minutes) measuring the primary and secondary endpoints, as well as the PHQ-9 (~5 minutes) for monitoring of mood symptoms.

The intermediate assessment visits will include the following study procedures:

- **Cognitive Tasks:**
- Digit Symbol Matching
- Multiple Object Tracking
- Digit Span Backwards
- Simple RT
- Choice RT
- Letter/Number Switch
- Gradual CPT
- **Functional Assessments:**
- NeuroQOL
- WHODAS (12-item)
- **Mood Symptom Scales:**
- PHQ-9

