7.1 Study Intervention/Device Description

The AKL-T01 intervention and the study assessments will be administered on an Apple iPad. The intervention video game is an iPad application that will be pre-installed on the iPads provided to participants. The iPad will also include shortcuts to the cognitive tasks and the RedCap database through which they will complete the self-report scales. All other applications and web pages will be locked on the intervention iPads. Participants in both the intervention arm and the waitlist control arm will be provided with iPads to ensure consistency in the data collection device.

The iPads will be shipped to participants' homes with a self-addressed return envelope for the iPad to be mailed back to the research team at the conclusion of participation in the study.

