7.4 Formulation, Appearance, Packaging, and Labeling

The devices provided to the participants will be Apple iPads. Participants will only be able to access the AKL-T01 video game interface (intervention arm only), the cognitive task battery, and the RedCap database for assessment administration. Participants will review instructions for using the iPads with a member of the research team during their first weekly check-in visit.

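### Randomisation precedes the week-0 battery, and one-arm gameplay training shares that visit in no stated order, so the primary baseline may be measured after the arm is known

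*Combined protocol and SAP*

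**What the plan says.** **Order of events.** Section 6.1.1 allocates eligible participants "1:1 using a computer-generated randomization scheme developed by the data manager at the conclusion of the screening visit". In Section 6.1, the table headed "Table 1. Schedule of trial events" marks randomisation in the screening column and nowhere else. The heading of 6.1.1 puts screening up to a week before randomisation, which does not quite match its own text, but neither version places allocation after the baseline battery.

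**Baseline.** Section 6.1.2.1 schedules the full battery, including Digit Symbol Matching and NeuroQOL, at week 0. Sections 1.2.4 and 12.4.1 define the primary endpoint as change from that value to week 6.

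**Training.** Section 6.1.2.1 adds: "Participants in the AKL-T01 intervention arm will be trained in procedures for gameplay during this visit". Section 2.4.3 gives its length: "Participants in the intervention arm will receive adequate training in gameplay (~45 minute training session with a member of the study team".

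**Staff.** For the week-0 visit, 6.1.2.1 says: "Participants in both arms will meet remotely with a member of the research team". On assessment, 2.4.3 says: "Assessment sessions will be conducted by PhD-level investigators of this study protocol or Research Assistants who have received extensive training in assessment administration".

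**Blinding.** Sections 3.1 and 7.11 state that participants cannot be blinded and that assessors will be. Section 7.11 also instructs participants and care managers not to disclose the arm to assessors, requires different assessors for the two periods of waitlist participants who cross over, and masks the analysts.

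**Device.** Section 7.1: "The intervention video game is an iPad application that will be pre-installed on the iPads provided to participants". Section 7.4: "Participants will only be able to access the AKL-T01 video game interface (intervention arm only".

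**The concern.** A baseline taken before allocation cannot be influenced by it. A baseline taken afterwards, in people who may already know their arm, has no such guarantee, and here that baseline is half of the primary outcome. Two routes are open. First, a participant who knows the arm may approach the tasks or rate everyday cognition differently. Second, one arm may sit the battery after a long training session that the other arm does not have. Either could produce a between-arm difference at week 0 that passes into the change score and cannot be told apart from a treatment effect or from chance imbalance.

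**Working it through.** The plan states no figure on this point, so the check is mainly a reading of the sections in sequence.

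1. **Is allocation before baseline?** Yes. Section 6.1.1 and Table 1 agree that it belongs to screening; the battery is at week 0 (6.1.2.1).
2. **Is the arm withheld until the battery is done?** No section says so. Sections 3.1 and 7.11 say that participants will know their arm but not when they are told.
3. **Could the device reveal it?** Yes. The same iPad carries the assessments and, in one arm only, access to the game (7.1, 7.4).
4. **Is training placed after the battery?** Section 6.1.2.1 mentions the battery first and training second, but only places both in the same visit. The battery takes about 35 + 30 + 10 = 75 minutes (6.1.2.1) and training about 45 minutes (2.4.3). Sections 2.4.1 and 13.1.1 list fatigue, frustration and headache among the risks of gameplay, and 2.4.1 attaches fatigue to the assessments too. The order therefore matters, and it is left open.
5. **Is the trainer separated from the assessor?** The week-0 contact and the trainer are each described only as a team member (6.1.2.1, 2.4.3). The non-disclosure instruction in 7.11 names participants and care managers, not the trainer. The only explicit separate-assessor rule concerns waitlist crossover.

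**How a week-0 difference enters the analysis.** Let s0 and s6 be the shifts (AKL-T01 minus waitlist) at weeks 0 and 6 that come from knowing the arm or, at week 0, from prior training. Let D be the true effect on change.

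- Change-score ANOVA (12.4.1): expected difference = D + s6 − s0.
- Random-intercept model with a group-by-time slope (Sections 10 and 12.2), assuming linear time and complete data at weeks 0, 2, 4 and 6: the mean time is 3, the deviations are −3, −1, 1 and 3, and their squares sum to 9 + 1 + 1 + 9 = 20. The weight of week 0 in the six-week slope is 6 × (−3)/20 = −0.9.

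The plan names both analyses. A week-0 shift enters the first in full and the second at 0.9, so the choice between them does not remove the issue. With a baseline that cannot depend on allocation, s0 = 0 and the first expression becomes D + s6.

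**The case against.** **The assessor blind is already required.** Section 7.11 makes assessors blind without exception. Anyone who trains one arm only knows the arm, so read strictly the trainer may not assess. Section 7.4 also places iPad instruction in the first weekly check-in, check-ins are with a care manager, and Table 1 marks an intervention/check-in contact at week 0. This largely stands: a reader might infer that the week-0 assessor is unblinded, but the documents do not say that. What is missing is an operational sentence that applies the rule to training. Nor would a lapse be confined to week 0: a person who trained a participant and later assessed that participant would still know the arm at weeks 2, 4 and 6.

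**The scores leave little room for influence.** The cognitive tasks are computerised (11.1), the self-report scales are completed on the iPad (7.1), and analysts are masked (7.11). This limits the route through the assessor. It does not close the route through the participant, or through training before the battery.

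**The change need not reduce bias.** This is correct. If s0 and s6 have the same sign, removing s0 lowers the absolute bias in the change score only when s6 is less than half of s0. A shift that is equal at both times cancels now and would not cancel afterwards. If the signs are opposite, removing s0 always helps. The documents do not show which pattern applies.

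**Conclusion.** The point holds as a design weakness that should be corrected: the written sequence allows a post-allocation baseline to enter the primary change score, and in one arm allows it to follow gameplay training. The conclusion rests on the absence of any rule on disclosure or order at week 0, not on evidence that a biased baseline will occur.

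The size and direction of any effect are unknown. A reader might infer a calculable rise in the false-positive rate, but the documents give neither the shifts nor the baseline to week-6 correlation, and any such figure would follow wholly from assumed values. The argument is that the baseline of a randomised comparison should not be able to depend on allocation. Expectancy bias at week 6, which comes from the unblinded waitlist design, is a separate limitation that this change does not address.

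**What to change.** Amend Sections 6.1.1, 6.1.2.1 and 7.11 and Table 1 together:

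- Complete and save the full week-0 battery before randomisation, and align the 6.1.1 heading with the new time of allocation.
- If device set-up requires earlier allocation, at minimum withhold both disclosure of the arm and access to the game until the battery is saved.
- In either case, hold gameplay training after the battery, given by an unblinded team member who does no assessments, such as a care manager. This puts into practice the assessor blind that 7.11 already requires at every visit.

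**Cost.** A protocol amendment, one reordered session, and a way to enable the game after baseline. The game is pre-installed, but access differs by arm and the documents describe no remote unlock. If none exists, a second shipment could be needed, so this should be settled before choosing between the first two options. Care managers are already unblinded and in weekly contact with participants, so the training can be assigned to an existing role.
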